### 7.1.2 Solicited ocular reactions

[figure not shown]
Solicited local reactions after TO administration are defined as AEs with the following PTs:

- Lacrimation increased
- Swelling of eyelid
- Ocular hyperaemia
- Ocular discomfort

occurring in the period after and up to and including 14 days after Day 28, Day 112, and Day 140 vaccinations.

The number and percentage of subjects and the number of events will be presented by PT:

- At Day 28 and Day 112 for the five TO treatment regimens
  - Cohort A2
  - Cohort B
  - Cohort D1

- Cohort E1
- Cohort F1
- At Day 140 for the 11 TO treatment regimens present, where the placebo cohort (F) will be regarded as one
  - Cohort A1
  - Cohort A2
  - Cohort B1
  - Cohort B2
  - Cohort C1
  - Cohort C2
  - Cohort D1
  - Cohort D2
  - Cohort E1
  - Cohort E2
  - Cohort F

The number and percentage of subjects with events occurring in the period after and up to and including 14 days after the Day 28 and the Day 112 vaccinations and the corresponding 95% CI will be presented by visit together with a pairwise comparison of number of subjects with events using Fishers exact test for the following:

- Cohort B vs Cohort A2
- Cohort B vs Cohort F1

All information will be listed.

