11.4.4 Safety analysis

The binary primary endpoints are:

- Solicited injection site reactions after IM and ID administration with the following PTs: injection site erythema, injection site pruritus, injection site pain, injection site swelling and injection site warmth
- Solicited ocular reactions after TO administration with the following PTs: lacrimation increased, swelling of eyelid, ocular hyperaemia and ocular discomfort

- Solicited systemic reactions after vaccination with the following PTs: body temperature increased, chills, myalgia and rash

The frequencies of the binary endpoints will be presented with the corresponding 95% CI.

These endpoints will be analysed by pairwise comparison of active treatment groups versus placebo in 2 x 2 tables (presenting number and percentage of subjects experiencing the criteria) using Fishers exact test. Also, active treatment groups will be compared similarly.

Adverse drug reaction will be presented descriptively by treatment group (number of subjects, percentage of subjects experiencing the event and number of events), in tables of system organ class and PTs in summary tables presenting each group in separate columns.

Vital signs are presented descriptively by treatment group and visit. Both absolute values and changes from baseline are presented both in tables and in box-plots by visit.

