#### 7.1.1 Solicited injection site reactions

Solicited injection site reactions after IM and/or ID administration are defined as AEs with the following PTs:

- Injection site erythema
- Injection site pruritus
- Injection site pain (covers both the lower level terms *injection site tenderness* and *injection site pain*)
- Injection site swelling
- Injection site warmth

occurring in the period after and up to and including 14 days after Day 0, Day 28, and Day 112 vaccination.

The number and percentage of subjects and the number of events will be presented by PT:

- At Day 0 for the four treatment regimens present

- Cohort A-C
- Cohort D
- Cohort E
- Cohort F
- At Day 28 and Day 112 for the 10 treatment regimens present
  - Cohort A1
  - Cohort A2
  - Cohort B
  - Cohort C
  - Cohort D1
  - Cohort D2
  - Cohort E1
  - Cohort E2
  - Cohort F1
  - Cohort F2

The number and percentage of subjects with events occurring in the period after and up to and including 14 days after the Day 0 vaccination and the corresponding 95% CI will be presented together with a pairwise comparison of number of subjects with events using Fishers exact test for the following:

- Cohort A-C vs Cohort D
- Cohort A-C vs Cohort E
- Cohort A-C vs Cohort F

All information will be listed.

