### 7.1.3 Solicited systemic reactions

[figure not shown]
Solicited systemic reactions after IM and/or ID administration are defined as AEs with the following PTs:

- Pyrexia
- Chills
- Myalgia
- Rash

occurring in the period after and up to and including 14 days after the Day 0, Day 28, and Day 112.

*Pyrexia* should be used as PT for temperatures above 38.3°C only, which is not as in the FDA guidelines presented in the protocol Appendix 1 stating temperatures above 38.0°C. For increased temperatures at or below 38.3°C, the PT *Body temperature increased* is used and thus not included as events. If the temperature is unknown, *Pyrexia* will be used, and the event included.

The number and percentage of subjects and the number of events will be presented by PT:

- At Day 0 for the four treatment regimens present
  - Cohort A-C
  - Cohort D
  - Cohort E
  - Cohort F
- At Day 28 and Day 112 for the 10 treatment regimens present
  - Cohort A1
  - Cohort A2
  - Cohort B
  - Cohort C
  - Cohort D1
  - Cohort D2
  - Cohort E1
  - Cohort E2
  - Cohort F1
  - Cohort F2

The number and percentage of subjects with events occurring in the period after and up to and including 14 days after the Day 0 vaccination and the corresponding 95% CI will be presented together with a pairwise comparison of number of subjects with events using Fishers exact test for the following:

- Cohort A-C vs Cohort D
- Cohort A-C vs Cohort E
- Cohort A-C vs Cohort F

All information will be listed.

[figure not shown]

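### The SAP gives intervals and tests on only some of the vaccination days it counts for the three solicited co-primary endpoints, and section 8 does not itemise what was left out of protocol 11.4.4

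*SAP*

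**What the plan says.** **Protocol 11.4.4** covers the three solicited endpoints together. On intervals: "The frequencies of the binary endpoints will be presented with the corresponding 95% CI". On tests: "These endpoints will be analysed by pairwise comparison of active treatment groups versus placebo in 2 x 2 tables", by Fisher's exact test, with active groups also compared with each other. It names no vaccination day and excepts none. It does not say whether an endpoint is scored per vaccination or once per subject over all vaccinations.

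**SAP 7.1.2 (ocular)** defines the endpoint over "14 days after Day 28, Day 112, and Day 140 vaccinations". Day 140 is tabulated by preferred term: "At Day 140 for the 11 TO treatment regimens present, where the placebo cohort (F) will be regarded as one". Intervals and Fisher tests (B vs A2 and B vs F1) are limited to "14 days after the Day 28 and the Day 112 vaccinations and the corresponding 95% CI will be presented by visit".

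**SAP 7.1.1 (injection site)** counts events up to "14 days after Day 0, Day 28, and Day 112 vaccination", but its intervals and tests (A-C vs D, vs E and vs F) cover only "14 days after the Day 0 vaccination and the corresponding 95% CI will be presented together with a pairwise comparison". **SAP 7.1.3 (systemic)** has the same structure: it counts "14 days after the Day 0, Day 28, and Day 112" and makes the same three comparisons after Day 0 only.

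**SAP section 2** says the SAP points out its departures from the protocol analysis in section 8. **Section 8** lists four items: the event windows, the pyrexia term, the added Wilcoxon tests, and a general remark that presentations and analyses were adapted to the data.

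**The concern.** These are co-primary safety endpoints, and the days without intervals matter to the objectives. Intradermal CTH522 is given only to Cohort C and only on Days 28 and 112. One primary objective (protocol 7.1) is the safety of CTH522 given by the ocular or intradermal route simultaneously with the intramuscular vaccine. For injection-site and systemic reactions the only days with intervals and tests come before any intradermal antigen is given.

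Day 140 is the one visit at which every cohort receives eye drops. Half of each active cohort gets antigen, the other half gets saline, and nothing is given by injection. The SAP spreads these data over 11 columns of counts. A reader of the report would have to combine columns and compute the intervals personally. Only by comparing the protocol with the SAP line by line would that reader learn that the planned analysis had been narrowed.

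**Working it through.** **Step 1. Days counted against days with an interval and test.**

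| Endpoint | Counted | Interval and test | Missing |
|---|---|---|---|
| Injection site (7.1.1) | 0, 28, 112 | 0 | 28, 112 |
| Ocular (7.1.2) | 28, 112, 140 | 28, 112 | 140 |
| Systemic (7.1.3) | 0, 28, 112 | 0 | 28, 112 |

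If protocol 11.4.4 is read per vaccination, the missing days are omitted outright. If it is read as one frequency over all vaccinations, no SAP interval covers that frequency either. The SAP covers less on both readings.

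**Step 2. Declaration.** The first item in section 8 concerns which events are counted, not which get intervals. The second and third concern the pyrexia term and the Wilcoxon tests. The last names no endpoint, day, interval or test. SAP 5.1 promises a difference, interval and p-value for tests that are run, so it adds nothing on a day with no test.

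**Step 3. Group sizes.** Protocol 11.4.3 gives 91% active and 9% placebo. 66 × 0.91 = 60.06 and 66 × 0.09 = 5.94, so 60 active and 6 placebo (60/66 = 90.9%, 6/66 = 9.1%), which reproduces the stated split. Sizes below that level are only in Figure 1, which is not shown. *Assumption:* equal splits, so 60/5 = 12 per active cohort, 6 per half, and 5 × 6 = 30 per arm at Day 140.

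**Step 4. Exact upper 95% limit with zero events,** 1 − 0.025^(1/n):

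| Group | Assumed n | Limit | Range |
|---|---|---|---|
| Half-cohort (one Day 140 column) | 6 | 45.9% | 52.2% to 41.0% for n = 5 to 7 |
| Cohort C, Days 28 and 112 | 12 | 26.5% | 30.8% to 21.8% for n = 10 to 15 |
| Pooled Day 140 arm | 30 | 11.6% | 13.7% to 10.0% for n = 25 to 35 |

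**Step 5. Is the Day 140 contrast interpretable?** By SAP Table 2, A2, B2, C2, D2 and E2 receive ocular CTH522 and A1, B1, C1, D1 and E1 receive ocular saline. V9 falls 26 to 30 days after V7, so its 14-day window does not overlap the previous one. Earlier treatment is identical between halves only in B and C. In A, D and E the earlier saline went to the eye in one half and into the skin in the other. B2 is at its third ocular antigen dose.

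**Step 6. Risk difference with zero events in both arms.** The Newcombe limit on each side is z²/(n + z²) = 3.84/33.84 = 11.4 points for 30 vs 30. With 25 vs 35 it runs from −9.9 (3.84/38.84) to +13.3 (3.84/28.84). Stratified over five cohorts of 6 vs 6 it is again ±11.4, and stratified Miettinen-Nurminen gives ±12.3. B and C alone give ±24.2. A Mantel-Haenszel Wald interval has zero variance here and collapses to a point.

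**Step 7. Testing power.** At assumed rates of 20% vs 5%, unstratified Fisher power runs from about 0.24 (30 vs 30) to 0.42 (29 vs 31) over all splits of 60 from 25 vs 35 to 35 vs 25. It jumps because the test is discrete, so no single value should be relied on. A 6 vs 6 comparison has power 0.06 even at 50% vs 10%.

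**The case against.** **Nothing is hidden.** Counts, percentages and event numbers are tabulated by regimen and all information is listed, so any arm's interval can be computed from the report. A reader might infer that Day 140 was dropped from the ocular endpoint. It was not. This stands, and it limits the loss to the intervals, the comparisons and the declaration.

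**The protocol never promised a separate Day 140 interval.** True: 11.4.4 names no day. But the SAP chose to report by visit and then gave intervals for only some of the visits it counts, and an overall reading is not honoured either.

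**The last item in section 8 covers it.** It does signal that analyses were adapted. It does not identify a change, so it does not do what section 2 says section 8 does.

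**The by-regimen tests would have told us nothing.** Largely right. At about 6 vs 6 almost no testing power was lost, the trial has no sample-size calculation, and SAP 7.7 already urges caution. That is a good reason for not running the tests. It is no reason to leave out the intervals or the explanation.

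**The pooled Day 140 contrast is not a protocol analysis.** Correct. It compares halves of active cohorts, whereas the protocol compares groups with placebo. It concerns eye drops given alone, not simultaneously with the injection. A reader might also take it for the most precise ocular estimate the design allows. It is not: ocular CTH522 at any visit covers all of B plus A2, C2, D2 and E2, 12 + 24 = 36 subjects under the same assumption, with a zero-event limit of 9.7%.

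**Conclusion.** The point holds as a gap in precision and transparency. For all three solicited co-primary endpoints the SAP gives intervals and comparisons on fewer days than it counts, and section 8 does not say so. Neither finding depends on group sizes. The most consequential gap is intradermal CTH522 in Cohort C, which belongs to a primary objective and gets no interval or comparison for injection-site or systemic reactions.

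The size of the gain at Day 140 does rest on the assumed equal splits: a zero-event upper limit of about 11.6% for a pooled arm, against 45.9% for a single column. The contrast cannot reliably detect a small excess, and the documents do not support a claim that useful power was lost. The change should be made, but it alters neither the conduct of the trial nor the data collected.

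**What to change.** 1. **SAP 7.1.1 and 7.1.3:** add exact (Clopper-Pearson) 95% intervals at Days 28 and 112 for the regimens already tabulated, including Cohort C.
2. **SAP 7.1.2:** add exact 95% intervals at Day 140. Keep the 11-column table and add one descriptive contrast, ocular CTH522 (A2+B2+C2+D2+E2) vs ocular placebo (A1+B1+C1+D1+E1), stratified by cohort. Use a risk-difference interval that does not collapse at zero events, such as stratified Newcombe, and an exact stratified test if a p-value is shown. Label it as an addition to the protocol that concerns eye drops given alone, and note the different saline route between halves in A, D and E. If Cohort F is added to the placebo arm, make that analysis unstratified: F has no CTH522 recipients and contributes nothing to a stratified test.
3. **SAP section 8:** declare by endpoint, day and cohort which intervals and comparisons from protocol 11.4.4 are still not carried out, with the reason.

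The cost is SAP wording and one or two more tables from data already collected. There is at most one more unadjusted test. The SAP now has 3 + (2 × 2) + 3 = 10 over the three endpoints, so this makes 11, under the caution in 7.7. The contrast mixes cohorts with different earlier vaccines. Stratification deals with that, but not with the saline-route difference. If the data are already unblinded, label the contrast post hoc and report the departures in the clinical trial report.

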11.4.3 Exposure and treatment compliance

It is planned that 91% of the subjects will randomise to receive the 85 µg CTH522-CAF01, 15 µg CTH522-CAF01, or 85 µg CTH522-CAF09b in addition to the successive administration of the non-adjuvanted CTH522 or the placebo. The other 9% of the randomised subjects will receive only the placebo consisting of 0.9% NaCl. Treatment compliance is documented as a drug accountability log.

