### 3.2 Trial Design

[figure not shown]
The trial is a phase I, double-blind, parallel, randomised, and placebo-controlled trial of the chlamydia vaccine, CTH522, in healthy adults. The trial will be conducted at Imperial College Healthcare NHS Trust, London, in the UK.

It is planned to randomly assign 66 subjects into 12 treatment groups in six Cohorts. Cohorts A-D investigate CTH522-CAF01 administered IM in two doses (85 µg and 15 µg). Cohort E investigates CTH522-CAF09b administered IM in one dose (85 µg). Cohort F is the placebo group (Figure 1). The enrolled subjects will complete 12 trial visits.

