### 3.2.1 Treatment labels

The cohort labels will be used as treatment labels in tables, figures, and listings as described in Table 2. Cohorts who had the same treatment at first, second and/or third vaccination will when relevant be grouped at timepoints where the treatments received were similar, and will be labelled accordingly:

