#### 5.1 Statistical Considerations

Baseline is defined as the last assessment with available data prior to the first administration of trial medication. Day 0 is the day of first administration with IMP. Assessments from scheduled visits will be presented when available, otherwise the first unscheduled visit succeeding the scheduled visit in question is used.

Categorical data will be summarized by treatment group, using number and percentages of subjects. For calculation of percentages the denominator will either be the number of subjects in the analysis set or the number of subjects in the analysis set with non-missing values. Continuous data will be presented using the number of subjects (n), mean, standard deviation (SD), median, minimum, and maximum if nothing else is stated. Both the absolute values and the change from baseline will be presented.

Descriptive statistics for all endpoints will be presented by treatment group and visit (if applicable) using observed cases, i.e., no imputation of missing data will be performed.

All statistical tests will be two-sided and performed on a 5 % significance level. Estimated treatment differences and 95 % confidence intervals (CI) will be presented together with the corresponding p-value.

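### At Days 28 and 112 the SAP compares cohort B's eye reactions only with A2 and F1 separately; D1 and E1 receive the same saline drops but enter no comparison, and a pooled contrast should be added

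*SAP*

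**What the plan says.** Safety of non-adjuvanted CTH522 given by the topical ocular (TO) route alongside the IM vaccine is a primary objective (Protocol 7.1, SAP 3.1.1). Solicited ocular reactions are a co-primary endpoint (SAP 7.1).

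SAP 7.1.2 lists five TO regimens at Days 28 and 112: A2, B, D1, E1 and F1. SAP Table 2 shows that only B receives CTH522 drops; the other four receive TO placebo, which is saline (Protocol 9.1). All five are tabulated by preferred term, with subjects, percentages and events, and all data are listed.

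The inferential part is a "pairwise comparison of number of subjects with events using Fishers exact test for the following" two contrasts, by visit: "Cohort B vs Cohort A2" and "Cohort B vs Cohort F1". No ocular test is planned at Day 140. SAP 5.1 sets the level: "All statistical tests will be two-sided and performed on a 5 % significance level". It also asks for estimated differences and 95% confidence intervals beside each p-value.

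On size, SAP 3.2 says: "It is planned to randomly assign 66 subjects into 12 treatment groups in six Cohorts". Protocol 11.4.3 gives the split: "It is planned that 91% of the subjects will randomise to receive the 85 µg CTH522-CAF01" (or one of the other two active IM vaccines), and "The other 9% of the randomised subjects will receive only the placebo consisting of 0.9% NaCl". Neither document gives a sample size calculation, an assumed event rate or a power figure.

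**The concern.** Four randomised subgroups receive saline drops at the same visits as cohort B's CTH522 drops, so all four are concurrent controls for the drop itself. The plan uses two of them, one at a time, and these are small: A2 is half of an active cohort and F1 is half of the placebo cohort. D1 and E1 contribute to no estimated difference, confidence interval or test.

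These two contrasts are the only planned comparison of the CTH522 drop with saline on a co-primary endpoint. With about six and about three controls, a moderate excess of eye reactions in B would usually not reach significance, and the interval for the difference would be wide. More than half of the relevant control subjects would have been observed but not used for that purpose.

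**Working it through.** **Inputs.** There are 66 subjects in 12 groups (SAP 3.2), with 91% active and 9% placebo (Protocol 11.4.3). The test is a two-sided Fisher test at 5% (SAP 5.1, 7.1.2). Group sizes are given only in Figure 1, which is not shown, so equal allocation is an assumption. Event rates are also assumptions.

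**Group sizes.** 0.91 × 66 = 60.06 and 0.09 × 66 = 5.94, so 60 active and 6 placebo. Five active cohorts give 60/5 = 12 each and 6 per half; F1 = 6/2 = 3. Hence B = 12, A2 = D1 = E1 = 6, F1 = 3, and saline-drop recipients number 6 + 6 + 6 + 3 = 21.

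**Share left out.**
- B vs A2 omits 15/21 = 71%.
- B vs F1 omits 18/21 = 86%.
- The two together omit D1 and E1: 12/21 = 57%.

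**Smallest significant result when no saline recipient reacts.** The two-sided p-value sums the hypergeometric probabilities of all tables no more likely than the one observed.
- Against F1: 9/12 vs 0/3 gives C(12,9)/C(15,9) = 220/5005 = 0.044. 8/12 gives 495/6435 = 0.077.
- Against A2: 7/12 vs 0/6 gives (792 + 396 + 12)/31824 = 0.038. 6/12 gives (924 + 72 + 1)/18564 = 0.054.
- Against all 21: 3/12 vs 0/21 gives C(12,3)/C(33,3) = 220/5456 = 0.040. 2/12 gives 66/528 = 0.125.

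**Precision of the saline rate.** With zero reactions, the exact 95% upper limit is 1 − 0.025^(1/n): 71% for n = 3, 46% for n = 6 and 16% for n = 21.

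**Power.** This is exact: the sum over all 2×2 tables with p ≤ 0.05 of Bin(x; 12, rate in B) × Bin(y; n, rate on saline).

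| Rate in B vs saline | B vs F1 (n=3) | B vs A2 (n=6) | B vs pooled (n=21) |
|---|---|---|---|
| 30% vs 5% | 0.2% | 3% | 48% |
| 40% vs 5% | 1% | 12% | 69% |
| 50% vs 5% | 6% | 30% | 85% |
| 30% vs 10% | 0.2% | 2% | 27% |
| 50% vs 10% | 5% | 23% | 67% |
| 50% vs 20% | 4% | 13% | 34% |
| 70% vs 10% | 36% | 65% | 93% |
| 80% vs 10% | 60% | 83% | 98% |

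**Sensitivity to group size.** B and A2 = D1 = E1 were set to 10 and 5, 11 and 5, 12 and 6, and 14 and 7, each with F1 = 2, 3 or 4.
- At 50% vs 5%, power is 0.3–9% (F1), 22–45% (A2) and 73–90% (pooled).
- At 50% vs 10%, it is 0.3–8%, 17–32% and 57–77%.
- The share in neither test is 53–61%.

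The pooled contrast has the highest power in every setting tried.

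**The case against.** This is a phase I trial without a sample size calculation, sized for a review of the safety profile (Protocol 11.4.8). SAP 7.7 says the Fisher tests should be interpreted with care, and SAP 5.1 already calls for differences and intervals, so a result would not be reported as a bare non-significant p-value. That stands, and it limits the weight of the point. But an interval built on three or six controls is wide for the same reason that the test is weak, and the caution in SAP 7.7 does not supply the missing comparison.

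The choice of contrasts is also defensible. A2 is the only saline-drop group with the same IM product and dose as B, and B vs F1 is the ocular comparison of active with placebo that Protocol 11.4.4 calls for. Both should stay. SAP 3.2.1 does not settle the case for pooling either: cohorts with the same treatment "will when relevant be grouped at timepoints where the treatments received were similar", whereas A2, D1, E1 and F1 had four different IM treatments. However, B vs F1 already differs in both drop and IM product, so a pooled contrast brings in no new kind of difference.

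A reader might infer more than the documents support:
- That the D1 and E1 data are unused. They are tabulated by preferred term and listed; they are absent only from the comparisons.
- That the planned tests have almost no power at all. At 80% vs 10% they have 60% and 83%.
- That pooling makes the comparison adequate. At 50% vs 20% it reaches only 34%.
- That B vs A2 would verify the pooling assumption. It cannot, because both groups receive the same IM product.

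**Conclusion.** The point holds as an inexpensive improvement, not as an error that invalidates the analysis. For the comparison of CTH522 drops with saline drops, the SAP leaves 12 of 21 concurrent saline-drop recipients (57%) out of both planned contrasts. For small to moderate differences this costs a great deal of power: at 50% vs 10%, 5% and 23% as planned against 67% pooled.

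The figures rest on equal allocation, because Figure 1 is not shown, and on assumed reaction rates, because the documents give none. The direction is the same at every group size and rate tried; the gain is smaller when reactions to saline are common. The pooled contrast also assumes that eye reactions to saline drops do not depend on the IM product.

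**What to change.** In SAP 7.1.2, keep B vs A2 and B vs F1. Add B vs all concurrent TO-saline recipients (A2 + D1 + E1 + F1) at Day 28 and at Day 112, with the difference, its 95% CI and the Fisher test, specified before unblinding. Footnote that the pooled controls differ in IM product. Show the reaction rates of A2, D1, E1 and F1 side by side; with groups this small, that is only a limited check on pooling.

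The cost is a few lines of SAP text and an extra column in the table, with no new data. The downsides are one more unadjusted comparison per visit, to be covered by the caution in SAP 7.7, and reliance on the pooling assumption.
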